5.2.3 Patient satisfaction endpoints

Patient satisfaction at discharge from ED/CPU

5.2.4 Health economy endpoints

Length of stay at the Emergency Room

Length of hospital stay in the CPU

Length of stay in an intensive care unit (ICU)

Total length of hospital stay including time as an inpatient on other wards

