Inclusion Criteria	Admission to the Emergency Department with symptoms consistent with ACS: - Typical chest pain (with or without ECG-changes, but no ST-elevation) suggestive of unstable angina or non-ST-elevated myocardial infarction (NSTEMI) - Troponin negative at admission according to the current clinical practice Patient willing and able to give written informed consent
Exclusion Criteria	Patients with ST-elevation myocardial infarction (STEMI) Continuing chest pain or recurrent episodes of chest pain under therapy High-risk patients with suspected ACS who need to be hospitalized for reasons independent of their initial troponin result Patients who need to be hospitalized for other medical reasons Patients in need of urgent life-saving interventions Patients under 18 years of age Patients with a life expectancy < 6 months Patients with any condition that leads the treating physician to not consider the patient eligible for the trial
Study endpoints	Primary Endpoint: Rate of MACE (all- cause death or survived sudden cardiac arrest, myocardial infarction, re-hospitalisation for acute coronary syndrome, acute unplanned PCI, coronary artery bypass grafting (CABG) and documented life-threatening arrhythmias (VF, VT, AV-block III)) within 30 days Copeptin vs. Control group Secondary endpoints: Efficacy endpoint of rate of Patients in whom coronary angiography is performed Rate of Patients requiring PCI due to their findings in cardiac catheterization. Rate of bleeding events at 30 and 90 days defined as non-CABG intracranial, intraocular, or retroperitoneal bleeding; access-site hemorrhage requiring intervention or resulting in a ≥ 5 cm diameter hematoma; reduction in hemoglobin concentration of ≥ 4 g/dL without or ≥ 3 g/dL with an overt bleeding source; reoperation for bleeding; or blood product transfusion. Further secondary endpoints evaluate efficacy, safety, cost effectiveness and patient satisfaction of the new process including length of stay in the hospital
Safety	All major cardiac adverse events (MACE) as defined in the protocol and bleeding complications as defined in the protocol will be assessed and documented for the duration of the study.

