7.1 General Patient Flow

Consecutive N-STEACS patients of the Chest Pain Unit with a negative Troponin T at admission will be invited to participate. Troponin T is tested as part of the standard management of patients with suspected acute coronary syndrome. Patients who give their written informed consent will be randomized into one of two study arms (experimental and standard management).

Experimental Arm: Further management dependent on Copeptin result

1. Patients of the above described characteristics who test **negative for Copeptin** at admission will be considered low-risk. In these patients we abstain from further ACS evaluation and instead discharge them into ambulant care. Before discharge patients will have a final visit to secure their well-being. The visit includes a physical examination, an ECG and an assessment for MACE and bleeding events.

Patients who show any signs and symptoms of an acute illness requiring in-hospital treatment will not be discharged (see withdrawal criteria 5.3). This decision is at the discretion of the attending physician.

To secure the patients safety they will be discharged into each co-operating network of resident cardiologists . Patients are to see a cardiologist within a maximum of 3 days after discharge (if discharge falls on a Friday), preferably on the next day after discharge. Further appointments will be at the discretion of the resident cardiologist (see 7.2).

2. Patients with the above described characteristics who test **positive for Copeptin** at admission will be managed as by standard practice i.e. patients will be evaluated as by standard of care abiding current guidelines for the management of patients with suspected ACS

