8.9 Additional 3 hour blood test

Patients can, on an optional basis, agree to an additional, study-related blood draw at 3 hours after their initial admission. This blood sample will be used to further evaluate the kinetics of Copeptin. Additionally, Troponin will be measured to compare the two markers in these samples.

Patients who agree to the blood draw have to give their separate written consent in a special box of the informed consent form (s. attachment).

9 Risk-benefit-assessment

Copeptin negative patients might experience major adverse cardiac events after discharge, which could have been prevented in case of hospital admission, due to unrecognized acute coronary syndrome.

Precaution:

Patients for this trial are very carefully selected. Patients with concomitant diseases or conditions which require a hospitalisation as well as patients with instable angina despite maximal therapy are excluded from participation. Thus, only stable, symptom-free patients will be discharged. We cannot exclude that of these patients, some will be at risk for ACS-related complications. As a precaution, patients will only be discharged after an appointment with one of our co-operating resident cardiologists has been made via the praxis-connect system as explained in section 7.1. Thus, the onward specialist care of these patients is guaranteed. The co-operating cardiologists will be well informed and trained in all trial-matters. All patients will be re-admitted to the Emergency Department upon any suspicion of risk for complications.

Copeptin positive patients might be regarded as high-risk patients and receive more intensive treatment.

Precaution:

Management of all patients will be closely monitored by the principal investigator of each site to assure suitable care and therapy.

Potential advantages for patients in the experimental arm:

Copeptin negative patients bypass further ACS evaluation and are prevented from hospitalization. Patients might be spared an unnecessary hospital admission and antithrombotic and anticoagulant treatment with their related hazards and side-effects. Patients will profit from the personal care by the resident co-operating cardiologist.

All patients will profit from the close and intense monitoring and follow-up by an experienced clinical research team.

Potential advantages for the general public:

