If the new processes are shown to be efficient, safe, cost effective and/or to improve patient contentedness this trial is a great benefit to the general public.

Additional 3 hour blood draw:

The 3 hour additional blood draw is a study related blood draw. If a venous catheter is in place, it can be used to draw the blood for this sample. Otherwise a new venous puncture is necessary which holds the small risk of pain at the puncture site, local nerve irritation, hematoma and very rarely vasovagal collapse. The risk will be minimized by putting well trained staff in charge of the blood draws.

10 Termination and subsequent treatment

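### The synopsis and section 9 speak of cost effectiveness, but the health-economy endpoints are only lengths of stay with no time window, and the outpatient care that early discharge adds is not collected

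*Protocol*

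**What the plan says.** **The aim.** The synopsis, under Study endpoints, states: "Further secondary endpoints evaluate efficacy, safety, cost effectiveness and patient satisfaction of the new process including length of stay in the hospital". Section 9, on benefit to the general public, has a conditional sentence that begins "If the new processes are shown to be efficient, safe, cost effective".

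**The measures.** Section 5.2.4 has four health-economy endpoints: "Length of stay at the Emergency Room", "Length of hospital stay in the CPU", time in intensive care, and "Total length of hospital stay including time as an inpatient on other wards". None has a start point, an end point or a statement on readmissions. No cost, outpatient contact or cost per outcome is named.

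**The pathway.** Under section 7.1, copeptin-negative patients in the experimental arm skip further ACS work-up and go home. For them, "Patients are to see a cardiologist within a maximum of 3 days after discharge", and later visits are left to that cardiologist. Section 9 adds: "All patients will be re-admitted to the Emergency Department upon any suspicion of risk for complications".

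**The data collected.** After discharge, the table in section 8.6 schedules only the MACE and bleeding assessment at 30 and 90 days. The calls in section 8.7 cover survival, MACE and bleeding. Hospital records are obtained after a death or a hospitalisation. Re-hospitalisation for ACS counts as an event in the primary endpoint (5.1) and among the safety endpoints (5.2.2), not as days.

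**The concern.** The experimental process shortens the first stay by discharging patients early, and it moves part of their care to the cardiologist's practice or to a later return to hospital. A set of endpoints that measures hospital time only, and most naturally only the first stay, gives that moved care the value zero. The outpatient visit is required only of early-discharged experimental patients, so the omission is not neutral between the arms.

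At stake is what the trial may conclude about resources. Length of stay is a sound measure for the secondary hypothesis in section 5, a shorter stay in the ED/CPU and hospital. It does not support a statement that the process is cost effective. If the data are not gathered during follow-up, no later analysis can supply them.

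**Working it through.** The protocol gives no economic figure to reproduce. The point rests on comparing sections; the arithmetic only shows a plausible range.

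**1. Aim against measures.** Cost effectiveness is named twice (synopsis, section 9). All four items in 5.2.4 are durations. The aim is wider than the measures.

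**2. Where displaced care would be recorded.**

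| Care after early discharge | Collected? | In a health-economy endpoint? |
|---|---|---|
| Required cardiologist visit (7.1) | No (8.6, 8.7) | No |
| Further visits and ambulatory tests | No | No |
| ED re-attendance without admission | No planned capture | Not stated |
| Readmission | Records obtained (8.7) | Not stated; no window in 5.2.4 |

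**3. What a SAP could settle.** It could set the window for total stay and draw readmission days from the records. It could not create data on visits, tests or unadmitted re-attendances.

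**4. Size, under assumptions.**

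Inputs from the protocol: the 6-9 h interval to the second troponin (4.1), used as a rough stand-in for the hospital time saved per early-discharged patient; six-week MACE rates of 7.8% in patients sent home and 6.4% in serially troponin-negative patients (14.2.2); 446 patients per arm (synopsis).

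Assumed: *d* = 2 to 7 days per readmission, with 3 for illustration; readmission rates *r* from 1% upwards; 50% to 77% of patients copeptin-negative.

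Uncounted hours per patient = *r* × *d* × 24. With *d* = 3:
- *r* = 2 points: 0.02 × 72 = 1.4 h
- *r* = 4 points: 0.04 × 72 = 2.9 h
- *r* = 7.8%, every MACE treated as a readmission, nothing subtracted for controls: 0.078 × 72 = 5.6 h

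Gross range: 0.01 × 2 × 24 = 0.5 h to 0.078 × 7 × 24 = 13.1 h. Applied to a whole arm, that is 446 × 0.02 = 9 to 446 × 0.546 = 244 bed-days.

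Only the between-arm difference matters. Taking 6.4% as a rough control rate, the net is 0.014 × 72 = 1.0 h at *d* = 3, with 0.7 h at *d* = 2 (0.014 × 48) and 2.4 h at *d* = 7 (0.014 × 168).

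Excess readmissions needed to cancel the 6-9 h saving = saving / (24 × *d*):
- *d* = 2: 6/48 to 9/48 = 12.5 to 18.8 points
- *d* = 3: 6/72 to 9/72 = 8.3 to 12.5 points
- *d* = 7: 6/168 to 9/168 = 3.6 to 5.4 points

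Required cardiologist visits, if every copeptin-negative patient is discharged and attends once: 446 × 0.50 = 223 to 446 × 0.77 = 343. The endpoints in 5.2.4 value all of them at zero.

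**The case against.** There is a good deal to say for the protocol.

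- **Readmission days are not excluded.** A reader might infer from 5.2.4 that a patient sent home after two hours and admitted the following week scores two hours. The text does not say so: there is no window, records of any hospitalisation are obtained, and a SAP may set the window. This stands. What remains is that the items follow one admission through its units, so index stay is the natural reading, and two analysts could compute different endpoints.
- **Readmission for ACS is visible elsewhere.** It is part of the primary endpoint and a separate 30-day safety endpoint. This stands for ACS events, but not for days in hospital, other causes or outpatient care.
- **The saving is not shown to vanish.** A reader might infer that total hospital time could well be unchanged or higher. The protocol's figures do not support that. The 5.6 h is gross of controls and still below 6-9 h; set against 6.4%, it falls to 1.0 h. At 3 days per readmission, an ACS excess large enough to cancel the saving would more than double either reference MACE rate and would show in the primary endpoint. The 6-9 h is a sampling interval, not a stay, so the real saving may be larger. Longer readmissions lower the threshold, but the protocol gives no readmission length.
- **The return rule covers both arms.** Sections 7.6 and 9 speak of study patients and all patients. It is not a cost peculiar to the experimental arm.
- **A shorter stay is not guaranteed by design.** Section 7.1 leaves discharge to the attending physician's judgement, and copeptin-positive patients follow standard care. Whether the arm as a whole stays for less time is a fair question.
- **Cost effectiveness is not a formal hypothesis.** That is true; it appears in one synopsis sentence and one conditional sentence. The wording is nevertheless wider than the endpoints, and uncollected outpatient data cannot be recovered.

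**Conclusion.** The point holds in a limited form. The protocol speaks of cost effectiveness while its health-economy endpoints are lengths of stay without a time window, and its follow-up does not collect the outpatient care that early discharge adds. The comparison could credit the experimental arm with savings that are partly displaced care.

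The amount is unknown. It depends only on the difference between arms in readmission time, re-attendances and outpatient contacts. On the assumptions above, the readmission part is about 0.7 to 2.4 h per patient net, using the two quoted MACE rates as if they were readmission rates in comparable groups, which they may not be. The protocol does not show that this would cancel the saving. The outpatient part is at least one required visit per early-discharged patient, all unrecorded.

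The primary endpoint and the length-of-stay hypothesis are unaffected. The change is worth making because it is cheap and must be made before follow-up data are gathered.

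**What to change.** 1. In 5.2.4, define total length of hospital stay as all ED, CPU, ICU and ward time from randomisation to day 30 and to day 90, including re-attendances and readmissions, in all randomised patients of both arms.
2. Keep index length of stay as a separate process measure for the secondary hypothesis in section 5.
3. At the existing 30- and 90-day calls, ask both arms about cardiologist visits, ambulatory cardiac tests and ED re-attendances, and add these to sections 8.6 and 8.7.
4. If these items are not collected, remove the cost-effectiveness wording from the synopsis and section 9 and limit the claim to length of stay.

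Cost: readmission time can use records already obtained, and the rest needs a few CRF fields and questions at calls already planned. Outpatient contacts will carry recall error, and the apparent saving may shrink. No clinical management changes.

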5.2.5 Predefined subgroup analysis

Male/female

GRACE-Score strata

Age strata

5.3 Endpoints Committee

The Endpoints Committee will be composed of cardiologists and ED physicians. This Committee is responsible for assessing the primary and secondary efficacy endpoints.

5.4 Study design

National, multi-centre, prospective open randomized controlled clinical trial. The treating physicians will be blinded to the test result of the investigational marker for the control group.

5.5 Timetable

Start of recruitment / Initiation

- February 2011

Estimated trial duration:

- 12/18 months

Recruitment will stop at each site when the proposed sample size has been reached.

6 Study population

Eligible men and women of full age, who are patients of the Emergency Departments and Chest Pain Units of the participating sites, will be enrolled in this trial. There will be no specific gender distribution as gender specific differences concerning efficacy and safety of the investigational diagnostic process are not to be expected.

6.1 Inclusion criteria

- Admission to the Emergency Department with symptoms consistent with ACS:
 - Typical chest pain (with or without ECG-changes, but no ST-elevation) suggestive of unstable angina or non-ST-elevated myocardial infarction (NSTEMI)
 - Cardiac Troponin negative at admission according to the current clinical practice
- Patient willing and able to give written informed consent

6.2 Exclusion criteria

- Patients with ST-elevation myocardial infarction (STEMI)
- Continuing chest pain or recurrent episodes of chest pain under appropriate therapy
- High-risk patients with suspected ACS who need to be hospitalized for reasons independent of their initial Troponin result
- Patients who need to be hospitalized for other medical reasons
- Patients in need of urgent life-saving interventions
- Patients under 18 years of age
- Patients with a life expectancy < 6 months
- Patients with any condition that leads the treating physician to not consider the patient eligible for the trial

6.3 Justification for the inclusion of minors and persons unable to consent (if applicable)

Not applicable

7 Description of the investigational process

See also BIC-8 Flowcharts (attachment 1)

7.1 General Patient Flow

Consecutive N-STEACS patients of the Chest Pain Unit with a negative Troponin T at admission will be invited to participate. Troponin T is tested as part of the standard management of patients with suspected acute coronary syndrome. Patients who give their written informed consent will be randomized into one of two study arms (experimental and standard management).

Experimental Arm: Further management dependent on Copeptin result

1. Patients of the above described characteristics who test **negative for Copeptin** at admission will be considered low-risk. In these patients we abstain from further ACS evaluation and instead discharge them into ambulant care. Before discharge patients will have a final visit to secure their well-being. The visit includes a physical examination, an ECG and an assessment for MACE and bleeding events.

Patients who show any signs and symptoms of an acute illness requiring in-hospital treatment will not be discharged (see withdrawal criteria 5.3). This decision is at the discretion of the attending physician.

To secure the patients safety they will be discharged into each co-operating network of resident cardiologists . Patients are to see a cardiologist within a maximum of 3 days after discharge (if discharge falls on a Friday), preferably on the next day after discharge. Further appointments will be at the discretion of the resident cardiologist (see 7.2).

2. Patients with the above described characteristics who test **positive for Copeptin** at admission will be managed as by standard practice i.e. patients will be evaluated as by standard of care abiding current guidelines for the management of patients with suspected ACS

7.2 Safety assurance: Praxis-connect

Praxis connect is an internet-based portal for the management of patient referrals between hospitals and private practices.

It can be used for exchanging patient data between different hospitals and private practises using an encoded SSL-connection between the clinical institutions and a data processing centre, securing data privacy.

Through Praxis connect the Emergency Department physicians can directly book appointments into co-operating cardiologist's appointment calendars. Additionally they can grant the cardiologist access to important patient documents. This system will be used at Charité study sites and can be offered to the other centers if necessary.

7.3 Description of investigational diagnostic test / Cut-off

Copeptin will be measured using the homogeneous sandwich fluoro-immunoassay B·R·A·H·M·S Copeptin KryptorPlus. The test has a detection limit of 0.5 pmol/L and a functional assay sensitivity (detected by inter-assay precision of 20% CV) of < 2 pmol/L. Test results are available after 14 minutes of incubation. In contrast to mature Vasopressin, Copeptin is stable in all matrices at room temperature for at least 7 days and at 4°C for at least 14 days. The assay therefore offers considerable advantages for the exact measurement of the Vasopressin production. Reichlin et al. used a Copeptin cut-off level of 14 pmol/L. Copeptin levels below this cut-off in combination with a troponin T level < 0.01 µg/L correctly ruled out acute myocardial infarction with a sensitivity of 98.8% and a negative predictive value of 99.7% [8]. To assure patient safety, we will use a cut-off level of 10 pmol/l to decide between negative and positive test results. In the Gutenberg Heart study Copeptin testing in 5000 individuals revealed a 95th percentile for Copeptin of 9.8 pmol/L. In the Copeptin trial by Keller et al., the highest sensitivity (88.2%) and NPV (94.6%) were achieved with 9.8 pmol/L as the cut-off [10]. The excellent negative predictive value at this cut-point is the basis for the safety of patients who are discharged based on their Copeptin levels.

7.4 Description of the standard diagnostic tests /Cutoff

Troponin I or T or high-sensitive Troponin T will be tested as by standard practice of care at the individual study sites. The initial Troponin test can be performed on Point-of-care devices to assure timely randomization.

Standard Troponin T will be considered positive at a level of or above 0.03µg/L.

High sensitive Troponin T will be considered positive at a cut-off level of above 0.014 µg/L

7.5 Standard process

Copeptin results will not be revealed to the treating physicians. Patients will be managed as by standard practice i.e. patients will be evaluated as by standard of care abiding current guidelines for the management of patients with suspected ACS.

7.6 Procedures in case of emergency

The Emergency Departments of the study sites are available on 7 days for 24 hours. All physicians of the Emergency Departments will be informed of the trial and will re-admit study patients to the ED if necessary.

8 Study procedures

See also BIC-8 Flowcharts

8.1 Recruitment / screening procedures

Screening:

The screening for eligible patients will take place in the Emergency Departments with adjacent CPU of the 3 study centers.

All patients with suspected acute coronary syndrome must be screened for eligibility and listed in a screening-log, stating their enrolment in the trial or reasons why a patient was not enrolled. Unless patients are enrolled in the trial this list will only contain the patients age, gender, Troponin result and reason(s) for not enrolling.

The screening process involves a check of the patient's medical history, the results of his/her physical examination , an ECG and a routine blood draw including the routine Troponin test on a Point-of-care-(POCT) device to be able to assess the patient for the fulfillment of the **Inclusion and Exclusion Criteria (see 6.1 and 6.2).**

